### Specimen Processing

In the laboratory, in a BSL2 biosafety cabinet, with BSL2+ conditions, the PneumoniaCheck will be processed according to Biosafety approved processes.

For processing, the filter is removed from the device (see **Figure 1** for location of the filter) and captured coughed droplets eluted from the filter as described in Attachment 1. The 300ul of specimen containing elution buffer will be divided in 3 aliquots (RNAZol will be added to one aliquot) for storage at -80°C until

## Detection of SARS-CoV-2 RNA and Biomarkers in Coughed Droplets from Patients with COVID-19 and Controls

testing. The Spin-X column and filter will also be stored at -80°C. The vials will be sprayed with 70% alcohol to inactivate any contaminating virus before storage.

**Specimen testing.** The RNAZol containing specimen will be tested with the CDC SARS-CoV-2 N1 and N2 primers according to the CDC online protocol. One of the other aliquots will be thawed and tested by multiplex Luminex or Simoa Quanterix system assays for cytokines and chemokines (e.g., the [Inflammation 20-Plex Human ProcartaPlex™ Panel](#), Invitrogen™, Waltham, MA, USA) and enzyme immune assay for surfactant A (Human surfactant Protein A ELISA Kit, Abbexa Ltd UK) according to the manufacturer's instructions. The specimens will also be tested for amylase by an enzymatic assay according to the manufacturer's instructions. Before biomarker testing, SARS-CoV-2 will be inactivated with an Environmental, Health and Safety Office approved method (e.g., heat-inactivation at 56°C for 30 min. protocol) and for novel biomarkers by mass spectrometry.

### **7. Data and Specimen Banking**

Data will be analyzed based on specimen identification number and group (e.g., COVID-19 patient, non-COVID-19 acute respiratory illness patient, control). Participants will be consented for future contact and use of data and/or specimens. At the completion of this study, we will store any remaining samples for possible future use. The remaining samples may be stored indefinitely and may be used for future studies of genetic causes of the disease. The samples will be stored at Emory Children's Center and Emory Labs.

The sample will be given a unique identification number and stored without participant name or other identifiers. Only the investigator will have a list to know which sample is linked to which patient and this list will be kept confidential in a secure location. If the investigator distributes these samples for research into the causes of the disease, it will be released with the unique identifier, but without any names or medical record numbers.

### **8. Sharing of Results with Participants**

In general, we will not give any individual results from the study of the samples. If we find something of urgent medical importance, we will inform the participant or the participant's primary care physician, although we expect that this will be a very rare occurrence.

### **9. Study Timelines**

Patients who consent to participate in the study will be instructed on method of collection and asked to collect 5 sets of 10 cough specimens over the next 24 hours with the same PneumoniaCheck device. In some cases, participants may be asked to collect additional samples at a later time period.

### **10. Inclusion and Exclusion Criteria**

We will enroll up to 75 adult SARS-CoV-2 PCR positive patients and up to 30 adult patients with a non-COVID-19 acute respiratory illness being treated either as inpatients or outpatients to participate in the study. We will also enroll up to 30 adult healthy controls. We will collect coughed specimens during 5 sessions of 10 or more coughs separated by at least 15 minutes. Patients who consent to participate in the study will be instructed on method of collection and asked to collect 5 sets of 10 cough specimens over the next 24 hours with the same PneumoniaCheck device. After specimen collection is completed, the device is transferred to the laboratory and stored for processing. For processing, the filter (see **Figure 1**) with the captured coughed droplets is removed from the device, captured droplets eluted from the filter, and the eluate and filter are stored at -80°C for later testing, PCR for SARS-CoV-2 RNA, multiplex Luminex and Simoa Quanterix system assays for biomarkers of inflammation, enzyme immunoassay (EIA) for surfactant A, and an enzymatic assay for amylase. The PCR results, positivity and CT values, in

## **Detection of SARS-CoV-2 RNA and Biomarkers in Coughed Droplets from Patients with COVID-19 and Controls**

---

COVID-19 patients will indicate the sensitivity of this specimen for detecting SARS-CoV-2 RNA and in non-COVID-19 patients and controls the specificity. The ratio of surfactant A to amylase indicate lung and upper respiratory contributions to the specimen for all groups. The multiplex Luminex and Simoa Quanterix system data will give biomarkers of inflammation for each group and differences between groups biomarkers associated with COVID-19. We will also test some specimens with mass spectrometry to identify novel biomarkers associated with COVID-19 lung disease.

### **11. Vulnerable Populations**

The population group for this study is adults age 18 and up. The study will initially be inclusive to English as a primary spoken language. At a later point, inclusion to other primary languages will be considered with available resources to that population group.

### **12. Local Number of Participants**

Up to 90 total participants will be accrued locally; taking into consideration those that consent but are not able are to provide specimens. Those that consent and are unable to provide specimens will be considered screen failures and not counted toward overall enrollment.

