## Detection of SARS-CoV-2 RNA and Biomarkers in Coughed Droplets from Patients with COVID-19 and Controls

### 1. Study Summary

Study Title	Detection of SARS-CoV-2 RNA and Biomarkers in Coughed Droplets from Patients with COVID-19 and Controls
Study Design	Single Center comparative trial with controls
Primary Objective	Determine the sensitivity and specificity of detecting SARS-CoV-2 RNA in cough-generated droplets captured with the PneumoCheck™
Secondary Objective(s)	Determine the value of detecting inflammatory cytokines and chemokines and other biomarkers in cough-generated droplets with PneumoniaCheck in evaluating disease in COVID-19 patients.
Research Intervention(s)/Interactions	Determine the value of PneumoniaCheck specimens for diagnosing SARS-CoV-2 infection and assessing disease state and understanding pathogenesis of disease.
Study Population	We will enroll up to 30 SARS-CoV-2 PCR positive patients and up to 30 patients with a non-COVID-19 acute respiratory illness being treated either as inpatients or outpatients to participate in the study. We will also enroll up to 30 healthy controls.
Sample Size	Up to 135 across all cohorts
Study Duration for individual participants	Those who consent to participate will have a cough specimen collected over the following 24 hours and asked to do 4 additional sets of 10 coughs into the same device
Study Specific Abbreviations/ Definitions	NA
Funding Source (if any)	Internal funding in addition to Georgia Tech grant

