## **23. Resources Available**

- The research group at ECC has its own recruitment staff and utilizes research databases to satisfy recruitment goals.
- This research will be ongoing until the goals for recruitment have been satisfied.
- We are a research facility in which all staff members have been adequately trained on the protocol and appropriate training credentials are on record.

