## Detection of SARS-CoV-2 RNA and Biomarkers in Coughed Droplets from Patients with COVID-19 and Controls

NA Single site study

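### The protocol states two different enrolment maxima for the same single-site study: 135 (75/30/30) in Section 10 and the Sample Size row, and 90 in the Study Population row (30/30/30) and Section 12.

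*Protocol*

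**What the plan says.** Four statements in the current protocol bear on the maximum enrolment.

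- **Section 10 (Inclusion and Exclusion Criteria):** "We will enroll up to 75 adult SARS-CoV-2 PCR positive patients", with up to 30 patients who have a non-COVID-19 acute respiratory illness and up to 30 healthy controls.
- **Section 1, Sample Size row:** "Up to 135 across all cohorts".
- **Section 1, Study Population row:** "We will enroll up to 30 SARS-CoV-2 PCR positive patients and up to 30 patients with a non-COVID-19 acute respiratory illness", followed by up to 30 healthy controls.
- **Section 12 (Local Number of Participants):** "Up to 90 total participants will be accrued locally".

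Three further statements decide how these can be read.

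- **Number of sites:** the Study Design row says "Single Center comparative trial with controls", and Section 24 says "NA Single site study".
- **Who is counted (Section 12):** "Those that consent and are unable to provide specimens will be considered screen failures and not counted toward overall enrollment".
- **End of recruitment (Section 23):** "This research will be ongoing until the goals for recruitment have been satisfied".

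**The concern.** The same cohort at the same site has two maxima, and so does the study as a whole. Two rows of one summary table disagree with each other.

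The primary objective is sensitivity and specificity. Sections 10 and 17 take sensitivity from the COVID-19 patients and specificity from the two comparison groups. Which ceiling governs therefore decides how much information each estimate can rest on.

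There is also a compliance issue. A 91st participant is permitted by Section 10 and exceeds the limit in Section 12. Section 23 ties the end of recruitment to goals it does not define, and the only recruitment numbers in the protocol are these conflicting maxima.

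**Working it through.** **Inputs.** Cohort maxima come from Section 10 (75, 30, 30) and from the Study Population row (30, 30, 30). Stated totals come from the Sample Size row (135) and Section 12 (90).

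**Reproducing the stated totals.**

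| Source of cohort maxima | Sum | Matches 135 (Sample Size row)? | Matches 90 (Section 12)? |
|---|---|---|---|
| Section 10 | 75 + 30 + 30 = 135 | Yes | No |
| Study Population row | 30 + 30 + 30 = 90 | No | Yes |

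Each set is consistent within itself, and the two contradict each other. The totals differ by 135 − 90 = 45. The COVID-19 maxima differ by 75 − 30 = 45, which is the whole of the gap.

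**Can the figures be reconciled?**

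1. *Local share of a larger total.* No. There is one site, so the local total is the study total.
2. *Screen failures.* No. Section 12 leaves people without a specimen out of the count. Allowing for them would put the number consented above the number enrolled. If the 90 were instead read as people consented, fewer than 90 would be enrolled whenever any of them failed to give a specimen, and the gap would widen.
3. *Ceilings, not targets.* Only in part. A total of 90 is compatible with any one cohort reaching its Section 10 maximum, but not with all three doing so.

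**What a cap of 90 implies for the Section 10 cohorts.** These are alternatives and cannot both occur.

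- All COVID-19 places filled: 90 − 75 = 15 comparison participants, out of 30 + 30 = 60.
- All comparison places filled: 90 − 60 = 30 COVID-19 patients, out of 75.

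**Illustration of precision.** The protocol gives no expected sensitivity or specificity, so the results below are assumed. The limits are exact (Clopper–Pearson) 95% limits: for x successes in n, the lower limit is the 0.025 quantile of Beta(x, n − x + 1) and the upper limit is the 0.975 quantile of Beta(x + 1, n − x).

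| Assumed sensitivity | n = 30 | n = 75 |
|---|---|---|
| About 70% | 21/30: 50.6–85.3% | 53/75: 59.0–80.6% |
| About 80% | 24/30: 61.4–92.3% | 60/75: 69.2–88.4% |
| About 90% | 27/30: 73.5–97.9% | 68/75: 81.7–96.2% |

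If the 75 COVID-19 places are filled under the cap instead, it is specificity that loses precision:

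| False positives | Lower limit, n = 15 | Lower limit, n = 60 |
|---|---|---|
| None | 15/15: 78.2% | 60/60: 94.0% |
| One | 14/15: 68.1% | 59/60: 91.1% |

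**The case against.** The strongest reply is that this is incomplete editing and not an open design question. The revision history records that the second amendment raised the COVID-19 sample from 30 to 75, an increase of 45 that equals the gap. Section 10 and the Sample Size row carry that change and the other two places do not, so a reader can infer that 135 is intended. That inference is reasonable, and it supports correcting towards 135. It does not remove the contradiction, which lies wholly in the current text.

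Several points on weight also stand.

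- All the figures are ceilings, and the protocol sets no precision target. The intervals above measure no failure of the plan.
- The 15-versus-60 case arises only if staff apply the amended cohort limit together with the unamended total.
- Section 23 does not define its goals, so treating the maxima as the stopping point is an inference.
- No sum in the protocol is miscalculated. The fault is inconsistency between sections.
- The first sentence of Section 12 says the 90 takes account of people who consent but give no specimen, while the next sentence excludes them from the count. Replacing the number alone would leave some doubt about who is counted.

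None of this yields a reading under which both 90 and 135 are right.

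**Conclusion.** The point holds. The protocol gives 135 in two places and 90 in two others for one single-site study. The difference is 45 participants, all of it in the COVID-19 cohort.

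The conclusion rests only on the stated figures, the single-site status and the counting rule in Section 12. It needs no assumption about test performance. The confidence intervals do rest on assumed results and serve only to show the scale of what the choice affects.

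The contradiction does not stop the study from running, and no stated power or precision target is missed. It should be fixed because the enrolment limit is a figure the study must work to. The limit accrual approved for the study is not visible in the protocol, so whether enrolling beyond 90 would breach it cannot be judged here.

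**What to change.** Carry the Section 10 figures through.

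1. In the Study Population row of Section 1, state maxima of 75 SARS-CoV-2 PCR positive patients, 30 patients with a non-COVID-19 acute respiratory illness and 30 healthy controls.
2. In Section 12, change the maximum from 90 to 135. Keep the rule that consented participants who cannot give a specimen are not counted, and word the opening sentence so that 135 plainly refers to counted participants.
3. Confirm that the approved accrual limit is also 135.

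The cost is wording corrections in two places by amendment, plus the check in item 3. No one is enrolled beyond the maxima already in Section 10, and endpoints, procedures and analysis are unchanged.

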### 5. Study Intervention/Investigational Agent

**Description:** The PneumoniaCheck is a device uses fluid mechanics to preferentially eliminate upper respiratory contaminants while capturing cough-generated droplets from the lung onto a filter. The device, illustrated in Figure 1 above.

**Device Handling:** The patient will be given the PneumoniaCheck device with a sterile ziplock bag and cooler with cold packs to keep the device, shown a video, given verbal guidance for collecting the first set of coughed specimens, and asked to do 4 additional sets of 10 coughs into the same device. The device will be stored in the ziplock bag in the cooler between collections.

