### 6. Procedures Involved:

Patients seen at Emory COVID-19 testing centers will be asked to participate in the study. Those who consent to participate will have a cough specimen collected over the following 24 hours and their medical record will be reviewed for age, sex, race/ethnicity, underlying medical conditions, their SARS-CoV-2 PCR test results, and other diagnostic test results if being seen for a COVID exposure or illness or other acute respiratory illness. The patient will be given the PneumoniaCheck device with a sterile ziplock bag and cooler with cold packs to keep the device, shown a video, given verbal guidance for collecting the first set of coughed specimens, and asked to do 4 additional sets of 10 coughs into the same device. The device will be stored in the ziplock bag in a cooler between collections. After the specimen is collected, the specimen will be collected by study personnel and transported using standard operating procedures for specimen transportation to the laboratory. In the laboratory, in a BSL2 biosafety cabinet with BSL2+ conditions, the PneumoniaCheck will be double bagged for storage at -80°C. Later the specimen is processed and tested for SARS-CoV-2 RNA by real time PCR and biomarkers by a multiplex Luminex assay and mass spectrometry. Each specimen will be given an identification number, without personal identifying information, which will be used to link laboratory results to clinical and epidemiologic data.

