### **13. Recruitment Methods**

Once the ECC-VRC staff learn of a potential participant, they may contact the patient's physician to determine whether the patient is suitable for participation in a research study. The study staff may contact the potential participant and the LAR to determine their interest in participating in the study. The staff may learn of potential participants either by reviewing test results in the medical records (for example, a positive diagnostic test) or from physician colleagues.

In the case of hospitalized patients, the patients' physician must be willing to act as the liaison between the patient, the patient's LAR and the research team. For outpatients, the primary physician may be asked to serve as the contact person for the patient. If the patient is ambulatory and has recovered from the illness, such patients may be asked to visit the ECC-VRC if they are interested in participating in the study. There will be no monetary incentive for the patient's physicians to refer patients to this study.

In the case of healthy volunteers, ECC staff will utilize the adult participant database for those who agreed to be contacted for future studies.

Research staff will utilize the Emory IRB approved Oral Consent form to prescreen interested participants. If the subject/LAR provides oral consent, the research staff will proceed with a prescreening telephone questionnaire to exchange relevant study information with the subject. Research staff will collect the participant's name, phone number, email, age, COVID history, respiratory history and medical history and offer time for questions and study information. If the subject/LAR is interested in participation, the first clinic visit will be made at which time full written consent or full oral consent (as stated in the consent section of this document) will be obtained prior to the initiation of any research activities.

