### **17. Data Management and Confidentiality**

**Data Analysis.** Data will be analyzed based on specimen identification number and group (e.g., COVID-19 patient, non-COVID-19 acute respiratory illness patient, control).

The quality of the specimen captured on the filter, i.e. from the lung or upper respiratory or both will be indicated by surfactant A (lung) and amylase (upper respiratory).

The PCR results will be analyzed as positive or negative and by CT value. The PCR results in COVID-19 patients will indicate the sensitivity of this specimen for detecting SARS-CoV-2 RNA and PCR results in non-COVID-19 patients and controls the specificity. The ratio of surfactant A to amylase indicate lung and upper respiratory contributions to the specimen for all groups. The multiplex Luminex data or Simoa Quanterix system will give biomarkers of inflammation for each group. We will also test some specimens with mass spectrometry to identify novel biomarkers associated with COVID-19 lung disease. Specimens will be saved for additional future research testing.

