## **Detection of SARS-CoV-2 RNA and Biomarkers in Coughed Droplets from Patients with COVID-19 and Controls**

4. Add 200ul Assay diluent to the 15ml tube with filter.
5. Mix well by vortexing for 2 min.
6. Transfer the filter and 200 ul of assay diluent carefully into the insert of a 2.0 ml spin-Xcolumns using the sterile forceps.
7. Add 100ul assay diluent to 15ml tube to remove any residual specimen. After vortexing for ~5 seconds, transfer the 100ul to the spin-X column containing the 200ul diluent andfilter.
8. Centrifuge the filter and diluent at 14,000rpm for 15 min.
9. Collect the clear flow through below the insert and divide into three aliquots. Add RNAZol to one the aliquots for PCR testing and store -80 freezer the 3 aliquots and the spin-X column with filter insert at -80°C until testing.

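### Section 12 removes consented participants who cannot produce a cough specimen as screen failures, so failures of the test procedure drop out of the study population and the reported sensitivity cannot by itself show diagnostic value

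*Protocol*

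**What the plan says.** Section 12 (Local Number of Participants) sets the accrual number "taking into consideration those that consent but are not able are to provide specimens", so the protocol expects such people. It then fixes their status: "Those that consent and are unable to provide specimens will be considered screen failures and not counted toward overall enrollment". Inability is not defined, and no sub-categories are given.

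The order of events is clear elsewhere. Section 13 says that full consent "will be obtained prior to the initiation of any research activities". Section 6 says: "Those who consent to participate will have a cough specimen collected over the following 24 hours". Section 5 describes a first set of coughs under verbal guidance, after which the participant is "asked to do 4 additional sets of 10 coughs into the same device". Section 10 defines the groups by adult age and by infection or illness status; it has no criterion on ability to cough.

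Section 17 defines the estimate: "The PCR results in COVID-19 patients will indicate the sensitivity of this specimen for detecting SARS-CoV-2 RNA". Section 10 says the same in substance. The goal in Section 2 is wider: the value of these specimens for diagnosing infection. Section 3 (Background) presents collection from patients without a productive cough as an advantage of the device.

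**The concern.** A screen failure is normally someone who turns out not to qualify. A PCR-positive adult who has consented, been given the device and cannot produce a specimen does qualify under Section 10. What failed is the test procedure. Under Section 12 this person leaves the enrolled population, and no other section brings the person back as a count, a denominator or an outcome.

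This matters because a diagnostic device can fail in two ways: it can yield a specimen that tests negative, or it can yield no specimen. Sensitivity from PCR results sees only the first. A reader who takes it as the share of infected patients the device would identify would overstate performance by the factor 1/(1 − f). The people set aside are also the ones who would test the dry-cough claim.

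**Working it through.** **Inputs from the protocol.** Up to 75 SARS-CoV-2 PCR-positive adults, 30 with another acute respiratory illness and 30 healthy controls (Section 10). The sum 75 + 30 + 30 = 135 agrees with the sample size in Section 1. Section 12's total of 90 does not, but that is a separate matter and plays no part here.

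**Inputs not in the protocol.** It states neither an expected sensitivity (Se) nor a collection-failure share (f), so there is no figure of the plan's own to reproduce. Both are assumed below.

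**Formulas.** Let f be the share of infected participants attempting collection who give no specimen.

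- Yield (failures counted as not detected) = Se × (1 − f)
- Gap = Se × f
- Ratio of sensitivity to yield = 1/(1 − f)

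**Illustration by counts.** Assume 60 positives among 75 specimens, plus k collection failures that do not use up the target of 75.

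| k | f = k/(75 + k) | Yield = 60/(75 + k) |
|---|---|---|
| 0 | 0% | 60/75 = 80.0% |
| 1 | 1.3% | 60/76 = 78.9% |
| 2 | 2.6% | 60/77 = 77.9% |
| 4 | 5.1% | 60/79 = 75.9% |
| 8 | 9.6% | 60/83 = 72.3% |

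**Range over assumed sensitivities.** Gap in percentage points:

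| f | Se 60% | Se 80% | Se 95% | 1/(1 − f) |
|---|---|---|---|---|
| 1% | 0.6 | 0.8 | 1.0 | 1.010 |
| 5% | 3.0 | 4.0 | 4.8 | 1.053 |
| 10% | 6.0 | 8.0 | 9.5 | 1.111 |

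**Value of a counted zero.** With no failures among n attempts, the exact two-sided 95% upper limit for f is 1 − 0.025^(1/n). For n = 75 this is 4.8%; for n = 30 it is 11.6%. A recorded zero beside 75 specimens would thus cap the gap at about 0.048 × 60 = 2.9, 0.048 × 80 = 3.8 or 0.048 × 95 = 4.6 points. Without a count no such bound can be given.

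**How common could failure be?** The protocol suggests it may be rare. The first set is guided. The eluate does not depend on the volume coughed: Attachment 1 says "Add 200ul Assay diluent to the 15ml tube with filter" and then adds a further 100 µl, and 200 + 100 = 300 matches Section 6, "The 300ul of specimen containing elution buffer will be divided in 3 aliquots". No validity threshold is stated. A returned device that has been coughed into will therefore probably give a PCR result.

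**The case against.** The strongest reply is that nothing is misestimated. Aim 1 concerns RNA in captured droplets, so sensitivity among specimens is the quantity asked for, and collection success is not an endpoint in Section 4. This stands, and specimen-based sensitivity should remain the Aim 1 result.

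Second, Section 12 is an accrual rule. It does not forbid recording reasons, and a participant-flow table may be left to an analysis plan. This stands in part: the absence of a table is no finding. But the classification is written into the protocol, and followed as written it places these people outside the study population that later tables would describe.

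Third, study-specific screening also follows consent, so a screen failure after consent is not in itself an error. That is true. The point rests on the order of events together with two further facts: collection is the index-test procedure, and no eligibility criterion has been failed.

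Fourth, the group may be nearly empty. The guided first set and the laboratory diluent make this plausible. It limits the size of the point, and it is also why a count would be cheap and informative.

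A reader might go further and infer that Section 12 pools failed attempts with people who never tried, and that this pooling makes sensitivity conditional. The documents do not support that. The text does not mention non-attempters, and Section 14 treats withdrawal separately. The conditionality arises because a PCR result needs a specimen and those without one are removed; separating the two kinds of people would leave the Aim 1 estimate unchanged.

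**Conclusion.** The concern holds as a minor one. Section 12 classes a failure of the index-test procedure as a failure of screening. The resulting sensitivity is sound for captured specimens, but alone it cannot support the goal of diagnostic value or the claim of collectability in dry cough.

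The size cannot be determined from the protocol. On assumed values it runs from nothing at f = 0, through about 4 points (80.0% to 75.9% with 4 failures beside 75 specimens), to 9.5 points at f = 10% with Se = 95%. The larger figures are illustrations, not expectations. They assume that a failed collection counts as not detected, which is one convention.

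A reader might also infer that the planned sensitivity is biased, or that many participants will be lost. Neither follows: the estimate matches its stated aim, and the protocol gives no failure rate.

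**What to change.** In Section 12, replace the screen-failure sentence with a statement that eligible consented participants who attempt collection but cannot provide a specimen stay in the study as collection failures, counted by group and reason, and do not use up the specimen target. Record three other outcomes as separate reasons, since none need mean inability to provide a specimen: no attempt or withdrawal; device not returned; and laboratory failure (specimen received but no PCR result).

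In Section 17, keep specimen-based sensitivity as the Aim 1 result. Report the collection-failure count and rate by group beside it. Add, as a supplementary figure labelled as one convention, sensitivity with collection failures counted as not detected.

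The cost is one reworded rule, a short addition to Section 17 and a small tally kept while collection is under way. The downside is a second, possibly less favourable, figure.
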